12.8 Statistical Analysis Plan

The primary analysis will be the modified ITT analysis for the primary endpoint of PFS at 18 months after randomization. The primary analysis will be performed using the Kaplan-Meier estimates for PFS for each arm at 18 months along with 95% confidence intervals. Several secondary analyses of PFS will be conducted, depending on an assessment of the original assumption of non-proportional hazards assumed in the study design. First of all, graphical and analytical diagnostics will be used to assess the presence of non-proportional hazards between treatment arms. If there is no evidence of nonproportional hazards, a relative risk will be estimated from the Cox model both unadjusted and adjusted for other covariates. To assess the effect of GVAX, several approaches will be taken: 1) inclusion of the treatment arm as a fixed covariate in a model, 2) inclusion of the total number of GVAX vaccinations (0-6) as a fixed covariate in a model, 3) treating the number of GVAX/placebo vaccinations as a time dependent repeated measures and an interaction between the number of vaccinations and the treatment arm in a model, 4) exploring a joint model for survival and longitudinal data. 26 If there appears to be non-proportional hazards, several analyses will be conducted: 1) a comparison of PFS at 18 months post randomization will be conducted using the linear combination test proposed by Logan et al.^{24, 28.29} This method directly compares the PFS curves starting at 18 months, and accounts for patients enrolled early in the study having additional follow-up past 18 months. 2) a pseudo value regression approach³⁰, 3) PFS from the start of vaccination will be analyzed, 4) multivariable cure rate model will be performed as described in Ibrahim et al.²⁷

Secondary objectives include relapse and non-relapse mortality (NRM), acute and chronic GVHD, overall survival. For the comparison of GVHD, NRM and relapse, we will perform competing risks data analysis using Gray test and competing risks regression analysis.²⁵ All laboratory correlative studies will be analyzed using appropriate statistical methods. In particular, the effect of vaccination on infiltration of dendritic cells, macrophages, granulocytes, and lymphocytes as well as T cell reconstitution will be examined by comparing pre to post vaccination data and the GVAX to the

placebo arm.

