3.0 PARTICIPANT SELECTION

3.1 Eligibility Criteria

Participants must meet the following criteria on screening examination to be eligible to participate in the study:

- 3.1.1 AML, MDS-RAEB (including CMML with excess blasts and MDS/MPN overlap syndrome) not in remission (defined as ≥ 5% blast in bone marrow or peripheral blood) prior to leukemia cell harvest. Patients may receive additional cytoreductive therapy after leukemia cell harvest and before admission for transplant, at the discretion of the treating physician. For patients with MDS-EB1(<10%blasts) or CMML-1, it is recommended that they proceed directly to transplant after the harvest if donor is available. If there is an extended delay, interval therapy with HMA is allowed.
 - 3.1.1.1 Patients may or may not have active disease at the time of transplant conditioning, but for RIC candidates, it is strongly recommended that disease is cytoreduced such that the pre-transplant admission marrow shows:
 - <30% blasts in a normocellular marrow (>=50% cellularity), or
 - <50% blasts in a hypocellular marrow (<50% cellularity)
- 3.1.2 HLA 8/8 or 7/8 matched related or unrelated donor available, as determined by antigen or allele level typing at HLA A, B,C, and allele level typing at HLA DRB1.
- 3.1.3 ECOG performance status 0-2.
- 3.1.4 Age ≥18 years. Because no dosing or adverse event data exist on the use of GVAX in participants <18 years of age, children are excluded from this study.
- 3.1.5 Patient deemed to be suitable candidate for myeloablative or reduced intensity conditioning allogeneic HSCT using PBSC or marrow as stem cell source.
- 3.1.6 Participants must have normal organ function as defined below:

Total bilirubin $\leq 2.0 \text{ mg/dL}$

(In patients with Gilbert's Syndrome, Total Bilirubin ≥ 2.0 is permitted)

AST (SGOT)/ALT (SGPT) \leq 3 X institutional upper limit of normal Serum creatinine \leq 2.0 mg/dL

- 3.1.7 The effects of GVAX on the developing human fetus are unknown. For this reason, women of child-bearing potential and men must agree to use adequate contraception (hormonal or barrier method of birth control; abstinence) prior to study entry and for the duration of study participation. Should a woman become pregnant or suspect she is pregnant while participating in this study, she should inform her treating physician immediately.
- 3.1.8 Ability to understand and the willingness to sign a written informed consent document.

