12.4 Randomization

After enrollment, patients will be randomized at a ratio of 1:1 between two arms using permuted block algorithm within strata. Randomization will be stratified by center (DFCI, BIDMC, MGH), disease (AML vs. MDS), age (≥50 vs. <50), and conditioning intensity (myeloablative Fly/Bu4 vs. RIC Flu/Bu2).

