12.5 Sample Size and Power Calculations

In our previous study¹⁰, the 2-year progression-free survival for 15 patients who received at least one vaccination was 46%. This estimate compared to 18% 2-year PFS from our contemporaneous control cohort that was most similar to those patients in the GVAX trial. Extrapolating this information, we hypothesize that the PFS will be increased by 75% at 18 months post randomization in Arm A (GVAX) compared to Arm B (placebo). A retrospective analysis of high risk AML/MDS patients who underwent myeloablative or RIC HSCT between 2004 and 2008 at DFCI shows that a small portion of patients are cured from the underlying disease after allogeneic HSCT and the distribution of PFS follows a two-component exponential cure rate model (Figure 1). Basing the fitted curve in Figure 1 as the null hypothesis, we hypothesize that the PFS will be increased by 75% from 26% to 46% by 18 months post HCT in Arm A. More specifically, the proposed alternative hypothesis is H_A: S_A > S_B,

where S_A and S_B denote the distributions of PFS in Arms A and B, as shown in (1) and (2), respectively

$$\begin{split} S_A &= 0.45 + 0.45 * exp(-t*(log(2)/2.5)) + 0.1*exp(-t*(log(2)/4.5)) \ (1) \\ S_B &= 0.24 + 0.76 * exp(-t*(log(2)/3.5)) \end{split} \tag{2}$$

This projection incorporates approximately 30-45 days of wait time from randomization to the start of GVAX/Placebo vaccination and additional ~40 days for the administration of a serial of 6 vaccinations. During this period, we expect little difference in PFS between two arms. Figure 4 depicts (1) and (2) graphically. With this design, 106 eligible patients with 69 events will be required to achieve approximately 80% power with one-sided significance level of 0.15. Since this is a direct but nondefinitive randomized comparison to a standard treatment control, we follow recommendations made by Rubinstein et al. ^{18, 19} and use a one-sided type I error rate of 0.15 with 80% power ¹⁸⁻²⁰. The power calculation is calculated using the R program, *Powlgrnk* (developed by [name] at DFCI), which computes power of the two-group log-rank test for arbitrary failure time distributions and has been used for non-proportional hazards alternative.²¹

[figure not shown]

Figure 4. Target PFS. Blue line represents the projected PFS distribution in Arm A (GVAX) and red line represents the projected PFS distribution in Arm B (Placebo). The solid black line is the Kaplan-Meier curve from the historical control

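### The primary 18-month PFS analysis uses none of the four randomisation strata; if those strata are prognostic, an unstratified comparison is mildly conservative and gives up about 0 to 3 points of power

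*Combined protocol and SAP*

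**What the plan says.** Section 12.4 (and 5.1.2): "Randomization will be stratified by center (DFCI, BIDMC, MGH), disease (AML vs. MDS), age (≥50 vs. <50), and conditioning intensity". Allocation is by permuted blocks: "patients will be randomized at a ratio of 1:1 between two arms using permuted block algorithm within strata". With three centers and three two-level factors there are 24 cells.

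Section 12.8 defines the primary analysis as: "The primary analysis will be performed using the Kaplan-Meier estimates for PFS for each arm at 18 months along with 95% confidence intervals". It names no stratum and no between-arm test. Section 12.5 does name a test, an unstratified two-group log-rank, and sizes the trial on it: "106 eligible patients with 69 events will be required to achieve approximately 80% power with one-sided significance level of 0.15".

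The other PFS analyses in section 12.8 are secondary and follow a check of proportional hazards. If hazards look proportional, a Cox model is fitted with and without covariates. If they do not, the list is a linear combination test of the curves from 18 months on, pseudo-value regression, PFS from the start of vaccination, and a multivariable cure model. No covariate is named in either branch.

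Section 12.1.1 limits the primary analysis to patients who receive at least one vaccination. Section 12.3 expects 30% of those enrolled not to reach that point (152 enrolled, 106 analysed).

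**The concern.** Blocked randomisation within strata makes the arms more alike on the stratification factors than simple randomisation would. If those factors predict PFS, the between-arm difference varies less than an unstratified standard error assumes. Confidence intervals are then somewhat too wide, the test rejects less often than its nominal level under the null, and some power is lost. Attrition before vaccination also undoes part of the balance, and an unstratified comparison cannot correct what imbalance remains.

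At stake are a few points of power in a 106-patient trial, and the freedom to choose covariates after seeing data, because the plan does not fix them.

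**Working it through.** **1. Reproduce the plan's figure.** Inputs from sections 12.2 and 12.5: 53 per arm, 3.8 years of accrual plus 18 months, one-sided 0.15, and curves (1) and (2).

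- Placebo: S_B(18) = 0.24 + 0.76 × 2^(−18/3.5) = 0.24 + 0.76 × 0.0283 = 0.262.
- GVAX: S_A(18) = 0.45 + 0.45 × 2^(−18/2.5) + 0.1 × 2^(−18/4.5) = 0.45 + 0.0031 + 0.0063 = 0.459.
- Simulated unstratified log-rank (30,000 trials): power 81.3% with 69.2 events, against the stated 80% and 69. The plan's figure reproduces.
- A simulated z-test of the 18-month Kaplan-Meier difference has 86.6% power. The two-proportion formula at 26% and 46% gives 87.1%.

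**2. Assumptions the documents do not supply.** Block size 4; AML 65%, RIC 60%, age 50 or over 75%, centers 60/15/25; 30% attrition at random and equal in both arms; a prognostic hazard ratio (HR) for each factor, varied below.

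**3. Type I error of unstratified comparisons, all four factors prognostic** (13,000 trials per setting; Monte Carlo SE = √(0.15 × 0.85/13,000) = 0.3 points; nominal 0.15).

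| HR per factor | Log-rank | 18-month z-test |
|---|---|---|
| 1.0 | 0.149 | 0.151 |
| 1.5 | 0.141 | 0.149 |
| 2.0 | 0.135 | 0.142 |
| 3.0 | 0.120 | 0.127 |

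The mechanism can be checked by hand. If the null standard deviation of Z is s, the true level is 1 − Φ(1.036/s). At HR 2 the simulated log-rank s is 0.931, so 1.036/0.931 = 1.113 and the level is 0.133. At HR 3, s = 0.88, which gives 1.178 and 0.120. Stratified tests stayed at about 0.14 to 0.16.

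**4. Four strata, disease by conditioning.** In the first set (8,000 trials, SE 0.4 to 0.5 points) the covariate effects are multiplied onto curves (1) and (2). Entries are unstratified → stratified, in percent.

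| HR disease / conditioning | Log-rank type I | Log-rank power | 18-month power |
|---|---|---|---|
| 1 / 1 | 15.2 → 15.4 | 81.5 → 80.3 | 87.4 → 87.2 |
| 2 / 1.5 | 14.4 → 15.0 | 78.5 → 78.7 | 84.1 → 85.5 |
| 2 / 2 | 14.2 → 15.4 | 75.4 → 76.6 | 82.0 → 84.1 |
| 2.5 / 2 | 13.6 → 15.0 | 74.1 → 76.8 | 81.2 → 84.4 |
| 3 / 3 | 13.0 → 15.0 | 69.2 → 73.2 | 75.0 → 80.1 |

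This construction moves the marginal PFS away from the design curves. Most of the fall down the table comes from that: at 2.5/2 log-rank power is 81.5 − 74.1 = 7.4 points lower, and stratifying recovers only 2.7 of them.

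With the marginal curves held at (1) and (2) (3,000 trials, SE about 0.7 points), unstratified log-rank power is 81.4% with no effect, 82.4% at 2/1.5 and 82.1% at 2.5/2, so it does not fall. The change in power from stratifying, in points:

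| HR disease / conditioning | Log-rank | 18-month contrast |
|---|---|---|
| 1 / 1 | −1.4 | −0.5 |
| 1.5 / 1.25 | −0.7 | +0.1 |
| 2 / 1.5 | +0.4 | +0.7 |
| 2.5 / 2 | +2.2 | +2.0 |

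A further run with the marginal curves held gave unstratified log-rank type I error of 0.147 (no effect), 0.139 (2.5/2) and 0.132 (3/3). Stratifying changed power by about −2 to +3 points (log-rank) and 0 to +3 points (18-month contrast).

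**5. All 24 cells.** 106/24 = 4.4 patients per cell; about 16 cells contain both arms. Log-rank power goes from 81.3% to 72.0% (HR 1.0 per factor), 82.5% to 74.3% (1.5), 83.7% to 78.6% (2.0) and 86.9% to 87.1% (3.0). Full stratification loses 5 to 9 points up to HR 2 and only breaks even near HR 3.

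**The case against.** The strongest reply is that the loss is small, conditional and in the safe direction. The documents give no hazard ratio for any stratum. At HR 1.5 per factor the 18-month test runs at 0.149, close to nominal. Conservatism does not create false positives in a comparison that section 12.5 itself calls nondefinitive. Attrition also erodes the balance that produces the conservatism. All of this stands, and it limits the point to a cheap improvement. The missing primary between-arm test is arguably the larger gap.

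Four stronger readings are tempting, and the documents do not support them:

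- **Type I error and power necessarily fall.** Both depend on prognostic strength that the documents do not give. With no effect the level is nominal, and with the marginal curves held as designed, unstratified power does not drop.
- **Covariates can enter only through a Cox model.** Section 12.8 lists pseudo-value regression and a multivariable cure model for non-proportional hazards. Beside the 18-month comparison it cites a reference whose title concerns directly adjusted survival curves. The gap is that these analyses are secondary and name no covariates.
- **Marrow status at the first vaccination belongs in the fix.** Section 3.1 does say "Patients may or may not have active disease at the time of transplant conditioning", so the population is mixed. But that marrow result is a post-randomisation measurement and not a stratum. The section 9.0 calendar lists it, while section 5.3 words it as optional. It is a separate question.
- **All four factors should be used as full strata.** At this sample size that usually costs log-rank power (step 5).

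**Conclusion.** The point holds in a limited form. The omission is plain from sections 5.1.2, 12.4, 12.5 and 12.8. Its size is modest and rests on assumed stratum shares, block size, prognostic strength and random attrition. For hazard ratios of 2 to 3 on disease and conditioning, nominal 0.15 becomes roughly 0.13 to 0.145; it reaches 0.12 for the log-rank only if all four factors carry a ratio of 3. The power given up is about 0 to 3 points with the design's marginal curves. It is 4 to 5 points only at 3/3, in the construction that departs from those curves. If the strata are not prognostic, nothing is lost by ignoring them.

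**What to change.** In section 12.8, name one primary between-arm comparison at one-sided 0.15:

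- D = Σ w_k [S_A,k(18) − S_B,k(18)], with stratum Kaplan-Meier estimates, weights w_k equal to each stratum's share of the analysed patients, and a within-stratum variance. Declare a benefit if D/SE exceeds 1.036. Weighting by stratum share keeps the target an overall 18-month difference.
- Use a few pooled randomisation strata, for example disease by conditioning (106/4 = 26.5 patients per cell on average). State in advance how a sparse cell is merged: with the assumed shares, MDS with myeloablative conditioning would hold 0.35 × 0.40 × 106 ≈ 15 patients.
- Use the same strata for any log-rank test, and report the unstratified result as a sensitivity analysis.
- Name the covariates for the secondary models.

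The cost is wording and standard software, since the strata are recorded at randomisation. If they carry no prognostic information, expect to lose about 0 to 0.5 points of power for the 18-month contrast and 1 to 2 points for the log-rank. The change should be fixed before the unblinding for analysis described in section 6.4.

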1.1 Study Design

GVAX vaccines will be generated by adenoviral vector mediated GM-CSF gene transfer into myeloblasts harvested from study subjects prior to admission for hematopoietic stem cell transplant Patients with Myelodysplastic syndromes (MDS) with excess marrow blasts or Acute myeloid leukemia (AML) not in remission are eligible. Leukemia cells will be harvested for vaccination generation after enrollment. Patients will be randomized (1:1) to GVAX versus placebo arm prior to The assignment of treatment arm will be blinded to the patients, treating transplant admission. physicians, nurses, research staff, and data assessors. Between the leukemia cell harvest and admission for allogeneic HSCT, patients are allowed to receive additional therapy (e.g. HMA therapy, chemotherapy etc.) at the discretion of the treating physician. Between day+30 to +60* after HSCT, patients with adequate hematologic recovery and no GVHD requiring systemic therapy will receive GVAX or placebo vaccine (normal saline) injections weekly x 3 week, then starting on week 5, every 2 weeks for 6 weeks, to complete a set of six total vaccinations. Patients will remain on tacrolimus for GVHD prevention during the vaccination period. Tacrolimus taper may commence after completion of vaccination, at the discretion of the treating physician, with the goal to be off immune suppression by 6-9 months post transplant in the absence of GVHD.

* Day 60 or next business day, if day 60 occurs on a weekend or holiday

1.2 **Primary Objective:**

Progression-free survival (PFS) at 18 months after randomization

1.3 Secondary Objectives:

- a) To assess the safety of vaccination following allogeneic (ablative or reduced intensity) stem cell transplantation
- b) To assess incidence of grade 2-4 and grade 3-4 acute GVHD, and chronic GVHD after vaccination following allogeneic stem cell transplantation.
- c) To assess PFS after start of vaccination
- d) To assess relapse and non-relapse mortality after vaccination
- e) To assess overall survival after vaccination
- f) To assess biologic activity of GVAX as compared to placebo vaccination after HSCT (see Section 8.0)

CONFIDENTIAL

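### The only between-arm test at 18 months and the only analysis for objective 1.3(c) hang on an unspecified proportional-hazards check

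*Combined protocol and SAP*

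**What the plan says.** Section 12.8 has two layers.

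- **Unconditional.** The primary analysis is the Kaplan-Meier estimate of PFS at 18 months in each arm, with 95% confidence intervals, in the modified ITT set. No between-arm test is attached to it. The log-rank test that supplies the power in section 12.5 is not mentioned in section 12.8.
- **Conditional.** Secondary PFS analyses follow from plots and formal checks of proportionality. On one side, "If there is no evidence of nonproportional hazards, a relative risk will be estimated from the Cox model", unadjusted and adjusted. That side also lists models with treatment arm, total vaccination count, a time-dependent vaccination count with an arm interaction, and a joint model. On the other side, if hazards look non-proportional, the plan lists the linear combination test at 18 months, pseudo-value regression, "3) PFS from the start of vaccination will be analyzed", and a cure-rate model.

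Section 1.3 states the corresponding secondary objective without any condition: "c) To assess PFS after start of vaccination". The paragraph on secondary objectives in section 12.8 covers relapse, non-relapse mortality, GVHD and overall survival, but not this one.

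Section 12.5 designs the trial on a non-proportional alternative. It says of its power program that it "has been used for non-proportional hazards alternative".

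**The concern.** The trial is designed on the expectation that hazards are not proportional. Its hypothesis is a difference in PFS at a fixed time, 26% against 46% at 18 months. Yet the formal comparison at that time is run only if a diagnostic, applied after the data are in, finds what the design already assumes. With about 69 events such a diagnostic has little power, so failing to reject is weak evidence of proportionality. The plan names no test, time transform or significance level, so the branch is also open to judgement once results by arm are visible.

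Two things are at stake: the formal between-arm comparison at the primary time point, and objective 1.3(c), whose analysis has no logical link to whether hazards are proportional. None of the models on the Cox side gives an 18-month contrast or PFS from first vaccination.

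**Working it through.** **Inputs.** From section 12.2: 53 patients per arm, accrual over 3.8 years (3.8 × 12 = 45.6 months), 18 months of further follow-up. From section 12.5: one-sided 0.15 and the two PFS curves, with t in months:

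- S_A(t) = 0.45 + 0.45·2^(−t/2.5) + 0.10·2^(−t/4.5)
- S_B(t) = 0.24 + 0.76·2^(−t/3.5)

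Assumption: uniform accrual, so follow-up runs from 18 to 18 + 45.6 = 63.6 months.

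**Step 1: reproduce the plan's figure.** Section 12.5 says "106 eligible patients with 69 events will be required to achieve approximately 80% power with one-sided significance level of 0.15".

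- S_A(18) = 0.45 + 0.0031 + 0.0063 = 0.459
- S_B(18) = 0.24 + 0.0215 = 0.262
- Ratio: 0.459/0.262 = 1.75, the stated 75% increase
- Expected events by 18 months: 53 × 0.541 + 53 × 0.738 ≈ 67.8; with staggered follow-up, 69.2
- Simulated log-rank power (10,000 trials): 80.4%, mean 69.3 events; a second seed gave 81.0% and 69.2

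The plan's power and event count reproduce.

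**Step 2: how non-proportional are the design curves?** The hazard is h(t) = −S′(t)/S(t).

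- Time 0: h_A = 0.45 × ln2/2.5 + 0.10 × ln2/4.5 = 0.1402; h_B = 0.76 × ln2/3.5 = 0.1505; ratio 0.93
- 6 months: h_A = 0.02975/0.5749 = 0.0517; h_B = 0.04587/0.4716 = 0.0973; ratio 0.53
- 18 months: h_A = 0.00181/0.4593 = 0.0039; h_B = 0.00426/0.2615 = 0.0163; ratio 0.24

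A single Cox hazard ratio fitted to such data has a median of about 0.63, which averages over this drift.

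**Step 3: how often would the check miss it?** The stand-in is a Grambsch-Therneau score test of the arm effect on simulated trials. The ranges cover Kaplan-Meier, identity and log time. The entries are the share of trials in which non-proportionality is not flagged.

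| Setting | 0.05 | 0.10 | 0.15 | 0.20 |
|---|---|---|---|---|
| Staggered follow-up, one test | 71–77% | 59–66% | 50–58% | 43–51% |
| All censored at 18 months, one test | 73–79% | 61–69% | 53–61% | 46–55% |
| Staggered, any of three transforms may flag | 63% | 50% | 41% | 34% |
| Only patients event-free at 2.5 months (assumed proxy for the vaccinated set), one test | 79–80% | 68–70% | 60–62% | 54–55% |

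Levels are two-sided. The span over reasonable rules is about 40–80%; the loosest rule shown goes somewhat lower.

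**Step 4: would an unconditional 18-month comparison cost power?** The standard error of the difference is √[(0.459 × 0.541 + 0.262 × 0.738)/53] = 0.0913, and the difference is 0.198. With z(0.85) = 1.036, power = Φ(0.198/0.0913 − 1.036) = Φ(1.13) ≈ 87%. A pooled-variance formula gives 86.6% and simulation 86–87%. The log-rank test has about 81% under the same curves.

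**Step 5: effect of the gate on the decision.** In 5,000 simulated trials (rank-time check at 0.05, a Kaplan-Meier z-test standing in for the 18-month test, one-sided 0.15), power was 81% for Cox, 87% for the unconditional 18-month test and 85% for the gated procedure. Gated and unconditional conclusions agreed in 95% of trials. With the check at 0.15, gated power was 86% and agreement 97%. Type I error of the gated procedure was about 0.15.

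**The case against.** The strongest reply is that the condition touches secondary analyses only. Both arms' 18-month PFS with confidence intervals is always reported, so a reader can form the difference and its standard error. **This stands.** A reader might infer from the gate that 18-month PFS itself could go unreported; section 12.8 does not support that. What is conditional is the formal test.

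A reader might also infer that the Cox branch yields one averaged hazard ratio and nothing else. It does not: it lists adjusted, vaccination-count, time-dependent and joint models. They still answer different questions from an 18-month contrast.

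Third, section 12.8 does not forbid the second list when hazards look proportional. True, but an analysis run off its branch would be unplanned.

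Fourth, the decision consequences are small, as Step 5 shows, and section 12.5 calls the comparison nondefinitive. This stands too, and it rules out any reading that the gate materially inflates type I error. Nor is it a fault that about 95% of trials take the Cox branch at 0.05 when the arms do not differ: hazards are then proportional.

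Fifth, the primary set already consists of vaccinated patients, so PFS from first vaccination concerns the same people. Partly fair. But the time origin moves from randomization before transplant to a date between day 30 and about day 60 after it, and section 1.3 lists this as an objective of its own.

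**Conclusion.** The point holds in this form. The plan's only formal between-arm comparison at 18 months, and its only analysis for objective 1.3(c), sit on a branch chosen by an unspecified diagnostic, in a trial whose own curves are non-proportional. That much is plain from sections 1.3, 12.5 and 12.8 and needs no simulation.

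The size depends on assumptions the plan does not supply. With one Schoenfeld-type test, the check misses the design's non-proportionality in about 71–77% of trials at 0.05 and 50–58% at 0.15, and in roughly 40–80% over reasonable choices. A reader might take a single figure near 70% as a property of the plan. It is not, because section 12.8 states neither test nor level, and graphical checks cannot be simulated. All these figures also assume the section 12.5 curves and uniform accrual.

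The harm is a planned test and a stated objective that may go unanalysed, not lost error control. It should be corrected, and correcting it is cheap.

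**What to change.** In section 12.8, before unblinding:

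1. Make the between-arm comparison of PFS at 18 months unconditional. State its one-sided level as 0.15, to match section 12.5, which says the design will "use a one-sided type I error rate of 0.15 with 80% power".
2. Make PFS from first vaccination unconditional and tie it by name to objective 1.3(c).
3. Report the Cox hazard ratio in all cases as a supportive average effect.
4. Use the proportional-hazards diagnostics only to describe how the hazard ratio changes over time, not to select analyses.

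The cost is SAP wording and a few more tables, with no new patients or data. Under the section 12.5 curves the 18-month comparison has about 87% power against about 81% for the log-rank test, so removing the condition need not cost power.
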